6.6 Dose Modifications for Toxicity

Adverse events (both non-serious and serious) associated with Pembrolizumab exposure may represent an immunologic etiology. These AEs may occur shortly after the first dose or several months after the last dose. Pembrolizumab must be withheld for drug-related toxicities and severe or life-threatening AEs as per Table 8 below. See Section 6.8 for supportive care guidelines, including use of corticosteroids.

Treatment discontinuation for AST, ALT deterioration in participants who present with Grade 2 AST or ALT will be triggered only if AST or ALT increases by greater than or equal to 50% relative to the measurement taken at initiation of systemic treatment (Cycle 1 Day 1) and lasts for at least 1 week.

Toxicity	Hold Treatment For Grade	Timing for Restarting Treatment	Treatment Discontinuation
Diarrhoea/ Colitis	2-3	Toxicity resolves to Grade 0-1	Toxicity does not resolve within 12 weeks of last dose or inability to reduce corticosteroid to 10 mg or less of prednisone or equivalent per day within 12 weeks
	4	Permanently discontinue	Permanently discontinue
AST, ALT, or Increased Bilirubin	2	Toxicity resolves to Grade 0-1	Toxicity does not resolve within 12 weeks of last dose
	3-4	Permanently discontinue (see exception below) ^a	Permanently discontinue
Type 1 diabetes mellitus (if new onset) or Hyperglycaemia	T1DM or 3-4	Hold Pembrolizumab for new onset Type 1 diabetes mellitus or Grade 3-4 hyperglycemia associated with evidence of beta cell failure	Resume Pembrolizumab when participants are clinically and metabolically stable
Hypophysitis	2-4	Toxicity resolves to Grade 0-1. Therapy with Pembrolizumab can be continued while endocrine replacement therapy is instituted	Toxicity does not resolve within 12 weeks of last dose or inability to reduce corticosteroid to 10 mg or less of prednisone or equivalent per day within 12 weeks
Hyperthyroidism	3	Toxicity resolves to Grade 0-1	Toxicity does not resolve within 12 weeks of last dose or inability to reduce corticosteroid to 10 mg or less of prednisone or equivalent per day within 12 weeks
	4	Permanently discontinue	Permanently discontinue
Hypothyroidism		Therapy with Pembrolizumab can be continued while thyroid replacement therapy is instituted	Therapy with Pembrolizumab can be continued while thyroid replacement therapy is instituted

Toxicity	Hold Treatment For Grade	Timing for Restarting Treatment	Treatment Discontinuation

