Infusion Reaction	2 ^b	Toxicity resolves to Grade 0-1	Permanently discontinue if toxicity develops despite adequate premedication
	3-4	Permanently discontinue	Permanently discontinue
Pneumonitis	2	Toxicity resolves to Grade 0-1	Toxicity does not resolve within 12 weeks of last dose or inability to reduce corticosteroid to 10 mg or less of prednisone or equivalent per day within 12 weeks
	3-4	Permanently discontinue	Permanently discontinue
Renal Failure or Nephritis	2	Toxicity resolves to Grade 0-1	Toxicity does not resolve within 12 weeks of last dose or inability to reduce corticosteroid to 10 mg or less of prednisone or equivalent per day within 12 weeks
	3-4	Permanently discontinue	Permanently discontinue
All Other Drug-Related Toxicity ^c	3 or Severe	Toxicity resolves to Grade 0-1	Toxicity does not resolve within 12 weeks of last dose or inability to reduce corticosteroid to 10 mg or less of prednisone or equivalent per day within 12 weeks
	4	Permanently discontinue	Permanently discontinue

Note: Permanently discontinue for any severe or Grade 3 drug-related AE that recurs or any life-threatening event.

^a For participants who begin treatment with Grade 2 AST or ALT at Cycle 1 Day 1 of treatment, if AST or ALT increases by greater than or equal to 50% relative to baseline and lasts for at least 1 week then participants should be discontinued.

^b If symptoms resolve within one hour of stopping IMP infusion, the infusion may be restarted at 50% of the original infusion rate (e.g., from 100 mL/hr to 50 mL/hr). Otherwise dosing will be held until symptoms resolve and the participant should be pre-medicated for the next scheduled dose.

^c Participants with intolerable or persistent Grade 2 drug-related AE may hold study medication at PI/delegate discretion. Permanently discontinue IMP for persistent Grade 2 adverse reactions for which treatment with IMP has been held, that do not recover to Grade 0-1 within 12 weeks of the last dose.

Table 8: Dose Modification Guidelines for Drug-Related Adverse Events

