6.8 Rescue Medications & Supportive Care

6.8.1 Supportive Care Guidelines

Participants should receive appropriate supportive care measures as deemed necessary by the PI/delegate. Suggested supportive care measures for the management of AEs with potential immunologic etiology are outlined below. Where appropriate, these guidelines include the use of oral or iv treatment with corticosteroids as well as additional anti-inflammatory agents if symptoms do not improve with administration of corticosteroids. Note that several courses of steroid tapering may be necessary as symptoms may worsen when the steroid dose is decreased. For each disorder, attempts should be made to rule out other causes such as metastatic disease or bacterial or viral infection, which might require additional

supportive care. The treatment guidelines are intended to be applied when the PI/delegate determines the events to be related to Pembrolizumab.

Note: if after the evaluation the event is determined not to be related, the PI/delegate does not need to follow the treatment guidance (as outlined below). Refer to Section 6.6 for dose modification.

It may be necessary to perform conditional procedures such as bronchoscopy, endoscopy, or skin photography as part of evaluation of the event.

6.8.1.1 Pneumonitis:

- For **Grade 2 events**, treat with systemic corticosteroids. When symptoms improve to Grade 1 or less, steroid taper should be started and continued over no less than 4 weeks.
- For **Grade 3-4 events**, immediately treat with intravenous steroids. Administer additional anti-inflammatory measures, as needed.
- Add prophylactic antibiotics for opportunistic infections in the case of prolonged steroid administration.

6.8.1.2 Diarrhoea/Colitis:

Participants should be carefully monitored for signs and symptoms of enterocolitis (such as diarrhoea, abdominal pain, blood or mucus in stool, with or without fever) and of bowel perforation (such as peritoneal signs and ileus).

- All participants who experience diarrhoea/colitis should be advised to drink liberal quantities of clear fluids. If sufficient oral fluid intake is not feasible, fluid and electrolytes should be substituted via IV infusion. For Grade 2 or higher diarrhoea, consider GI consultation and endoscopy to confirm or rule out colitis.
- For **Grade 2 diarrhoea/colitis**, administer oral corticosteroids.
- For **Grade 3 or 4 diarrhoea/colitis**, treat with i.v. steroids followed by high dose oral steroids.

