- When symptoms improve to Grade 1 or less, steroid taper should be started and continued over no less than 4 weeks.

6.8.1.3 Type 1 diabetes mellitus (if new onset, including diabetic ketoacidosis [DKA]) or \geq Grade 3 Hyperglycaemia, if associated with ketosis (ketonuria) or metabolic acidosis (DKA)

- For **T1DM or Grade 3-4 Hyperglycemia**
 - Insulin replacement therapy is recommended for Type 1 diabetes mellitus and for Grade 3-4 hyperglycaemia associated with metabolic acidosis or ketonuria.
 - Evaluate participants with serum glucose and a metabolic panel, urine ketones, glycosylated hemoglobin, and C-peptide.

6.8.1.4 Hypophysitis:

- For **Grade 2 events**, treat with corticosteroids. When symptoms improve to Grade 1 or less, steroid taper should be started and continued over no less than 4 weeks. Replacement of appropriate hormones may be required as the steroid dose is tapered.
- For **Grade 3-4 events**, treat with an initial dose of IV corticosteroids followed by oral corticosteroids. When symptoms improve to Grade 1 or less, steroid taper should be started and continued over no

less than 4 weeks. Replacement of appropriate hormones may be required as the steroid dose is tapered.

6.8.1.5 Hyperthyroidism or Hypothyroidism:

Thyroid disorders can occur at any time during treatment. Monitor participants for changes in thyroid function (at the start of treatment, periodically during treatment, and as indicated based on clinical evaluation) and for clinical signs and symptoms of thyroid disorders.

- **Grade 2** hyperthyroidism events (and **Grade 2-4** hypothyroidism):
 - In hyperthyroidism, non-selective beta-blockers (e.g. propranolol) are suggested as initial therapy.
 - In hypothyroidism, thyroid hormone replacement therapy, with levothyroxine or liothyroinine, is indicated per standard of care.
- **Grade 3-4** hyperthyroidism
 - Treat with an initial dose of IV corticosteroid followed by oral corticosteroids. When symptoms improve to Grade 1 or less, steroid taper should be started and continued over no less than 4 weeks. Replacement of appropriate hormones may be required as the steroid dose is tapered.

6.8.1.6 Hepatic:

- Comprehensive guidance on the diagnosis and management of hepatic events of interest are reported in Section 6.8.3.
- For **Grade 2** events, monitor liver function tests more frequently until returned to baseline values (consider weekly).
 - Treat with IV or oral corticosteroids

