- For **Grade 3-4** events, treat with intravenous corticosteroids for 24 to 48 hours.
- When symptoms improve to Grade 1 or less, a steroid taper should be started and continued over no less than 4 weeks.

6.8.1.7 Renal Failure or Nephritis:

- For **Grade 2** events, treat with corticosteroids.
- For **Grade 3-4** events, treat with systemic corticosteroids.
- When symptoms improve to Grade 1 or less, steroid taper should be started and continued over no less than 4 weeks.

6.8.1.8 Immune-related adverse events:

Please see Section 6.8.2 below regarding diagnosis and management of adverse experiences of a potential immunologic etiology.

6.8.1.9 Management of Infusion Reactions:

Signs and symptoms usually develop during or shortly after drug infusion and generally resolve completely within 24 hours of completion of infusion.

Table 9 below shows treatment guidelines for participants who experience an infusion reaction associated with administration of Pembrolizumab.

NCI CTCAE Grade	Treatment	Premedication at subsequent dosing
Grade 1 Mild reaction; infusion interruption not indicated; intervention not indicated	Increase monitoring of vital signs as medically indicated until the subject is deemed medically stable in the opinion of the investigator.	None

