- If the participant is clinically stable, Pembrolizumab dosing may be interrupted for up to 12 weeks. Subjects should undergo weekly laboratory tests including: AST, ALT, ALP, Tbil, Dbil, INR, HBsAg, HBV DNA (if detected at the onset of the flare). Obtain anti-HBe, anti-HBs, and HBV DNA levels (if not detected at the onset of the flare) every 2-3 weeks.
- If ALT returns to normal or Grade 1 (if normal at baseline), or to baseline grade (if Grade 2 at baseline) within 12 weeks, and participants are clinically stable, participants may restart Pembrolizumab treatment. If these conditions are not met, then Pembrolizumab treatment should be permanently discontinued.

b. Hepatitis C Recurrence or Flare

Participants who achieved a sustained virologic response at 12 weeks on specific antiviral treatment (SVR 12) and subjects with on-going HCV infection are eligible for enrolment. In rare circumstances, HCV participants who achieve SVR 12 may relapse at later time points. Relapse is characterised by detection of HCV RNA, often accompanied by ALT elevations to $>5\times\text{ULN}$. In the absence of hepatic decompensation, ALT/AST elevations are typically isolated (i.e., limited/no elevations of bilirubin/ALP).

Among participants with uncontrolled hepatitis C, virologic flares are possible. Hepatitis C flares are characterized by rapid elevations of ALT and AST to $>5\times\text{ULN}$ and/or $>3\times$ baseline along with a rise in HCV RNA. ALT elevation to $\geq 10\times\text{ULN}$ and a 1 log elevation in HCV RNA level are common. In the absence of hepatic decompensation, ALT/AST elevations are typically isolated (i.e., limited/no elevations of bilirubin/ALP). Laboratory abnormalities secondary to flare or recurrence are typically observed for 3-5 weeks.

Guidelines for participants with recurrent HCV infection or an HCV flare are described below:

i. Recurrent HCV infection:

If the participant entered the study with an HCV RNA test of “Target not Detected” and has confirmed detectable HCV RNA (2 specimens, 1 week apart), then the subject has experienced a late HCV relapse or a recurrent infection.

- Question the participant about use of injection or inhalation drugs
- At the time of first detection of HCV RNA, send a specimen for HCV genotyping
- Measure AST, ALT, ALP, Tbil, Dbil, and INR weekly
- Measure HCV RNA levels every 2 weeks
- Therapy with HCV anti-viral treatments should be strongly considered.

ii. HCV Flare:

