- At the time of first detection of HCV RNA, send a specimen for HCV genotyping
- Measure AST, ALT, ALP, Tbil, Dbil, INR weekly
- Measure HCV RNA levels every 2 weeks
- Therapy with HCV anti-viral treatments should be strongly considered.

iii. For both recurrent infection and HCV flare: if ALT returns to normal or Grade 1 (if normal at baseline), or to baseline grade (if Grade 2 at baseline) within 12 weeks, and the participants are clinically stable, participants may restart Pembrolizumab treatment. If these conditions are not met, then Pembrolizumab treatment should be permanently discontinued.

c. Immune-related hepatitis

i. Description: Immune-related hepatitis due to Pembrolizumab should be suspected if any of the following is seen:

- AST or ALT baseline values are less than 2×ULN, and AST or ALT laboratory values increase to $\geq 5\times$ ULN
- Among participants with Day 1 ALT or AST $\geq 2\times$ ULN, levels increase to $>3\times$ the Day 1 level
- AST/ALT >500 U/L regardless of baseline level
- Among participants with Day 1 Tbil levels <1.5 mg/dL: a value of >2.0 mg/dL
- Among participants with Day 1 Tbil levels that are ≥ 1.5 mg/dL: a value of $\geq 2\times$ the Day 1 level
- Total bilirubin >51.3 μ mol/L regardless of baseline level.

Immune-related hepatitis is a diagnosis made after excluding other possible etiologies for the change. Viral flare (if applicable), biliary or vascular obstruction, infection, medications, and alcohol use must be ruled out (see below).

ii. Management

- Interrupt Pembrolizumab treatment and alert the sponsor/CI or delegate as per ECI criteria above for ALT, AST, bilirubin, and hepatic decompensation.
- Start IV corticosteroid (methylprednisolone 125 mg) followed by oral corticosteroid (1-2 mg/kg/day).
- Monitor with biweekly laboratory tests including AST, ALT, Tbil, Dbil, ALP, and INR.
- If symptoms and laboratory tests resolve to Grade ≤ 1 or baseline (if abnormal at baseline), taper steroids over 28 days. Pembrolizumab treatment may be restarted after steroid treatment has been tapered to prednisone ≤ 10 mg/day (or equivalent dose of another agent). Treatment and laboratory results must be documented.

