- If laboratory abnormalities do not resolve within 3 weeks, or steroids cannot be lowered to ≤ 10 mg/day (or prednisone equivalent) within 12 weeks, or participants show evidence of decompensation to Child-Pugh C status or have esophageal or variceal bleeding at any point, treatment must be permanently discontinued. This must be documented.

d. Other Hepatic Events of Clinical Interest

- Infection needs to be ruled out with cultures of blood, urine, and ascites (if possible), as well as chest x-ray and abdominal imaging if relevant. If an infection is found, antibiotics should be started.
- If Tbil is elevated above baseline, magnetic resonance cholangiopancreatography or ultrasound with doppler should be obtained to rule out vascular compromise, biliary obstruction, and/or tumour progression. If biliary obstruction is present, consultation with a gastroenterologist and/or an interventional radiologist should be obtained to see if the obstruction may be relieved.
- A careful review of drugs, including herbal and alternative medications, should be obtained, and alcohol use should be ruled out.

- For all of these cases, participants may resume Pembrolizumab treatment if they are clinically stable after appropriate therapy or discontinue the causative agent, as long as laboratory values have returned to Grade 1 or baseline (if normal or Grade 1 at start) or to baseline grade within 3 weeks.
- Treatment must be permanently discontinued if the participant is off Pembrolizumab therapy for infection, obstruction, or drug/alcohol-related toxicity for more than 3 weeks, or if they have oesophageal bleeding, or become Child-Pugh C at any point.

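### The hepatic steroid taper trigger in Section 6.8.1.6 has no return-to-baseline option, unlike the taper rule in 6.8.3(c), although Grade 2 AST/ALT at Cycle 1 Day 1 is foreseen

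*Combined protocol and SAP*

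**What the plan says.** Section 6.8.1.6 covers steroid treatment of hepatic events. Its taper rule is: "When symptoms improve to Grade 1 or less, a steroid taper should be started and continued over no less than 4 weeks". No alternative is given for a participant whose baseline was already above Grade 1. Baseline does appear in the same subsection, but only for monitoring of Grade 2 events: "monitor liver function tests more frequently until returned to baseline values (consider weekly". The first bullet of 6.8.1.6 refers the reader to Section 6.8.3 for fuller guidance on hepatic events of interest.

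Section 6.8.3(c), on immune-related hepatitis, governs the same action. It applies when symptoms and laboratory tests have come down to Grade 1 or below "or baseline (if abnormal at baseline), taper steroids over 28 days".

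Abnormal baselines are expected. Table 2 in Section 4.1.1 admits AST and ALT up to 5xULN. Section 6.6 states: "Treatment discontinuation for AST, ALT deterioration in participants who present with Grade 2 AST or ALT will be triggered only if" the value rises by at least 50% from Cycle 1 Day 1 and stays there for at least a week. Table 8 footnote a repeats this, beginning "For participants who begin treatment with Grade 2 AST or ALT at Cycle 1 Day 1 of treatment". The Table 8 criterion for restarting pembrolizumab after a Grade 2 AST/ALT event is resolution to Grade 0-1, also with no baseline option.

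**The concern.** Two rules for starting a hepatic steroid taper sit in the same chapter and do not match. The mismatch matters for a participant who starts pembrolizumab with Grade 2 AST or ALT, has a further rise judged related to the drug, receives steroid, and then recovers fully to the starting value. That participant is as well as at entry but is still Grade 2. If the grade in 6.8.1.6 means laboratory grade, the taper is not triggered.

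What is at stake is avoidable steroid exposure in people with limited liver reserve, in a trial that otherwise restricts systemic glucocorticoids (Section 6.7.3). Under Table 8, the same participant could also finish steroid treatment and still not meet the wording for restarting pembrolizumab.

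**Working it through.** The plan gives no figure to reproduce, so the check is a comparison of texts.

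| Place | Action | Judged on | Threshold | Baseline option |
|---|---|---|---|---|
| 6.8.1.6 | Start taper | Symptoms | Grade 1 or less | No |
| 6.8.3(c) | Start taper | Symptoms and laboratory tests | Grade 1 or less | Yes, if abnormal at baseline |
| Table 10 | Consider taper, irAEs not covered elsewhere | Symptoms | Grade 1 or less | No |
| Table 8, Grade 2 AST/ALT | Restart pembrolizumab | Toxicity grade | Grade 0-1 | No |
| 6.8.3(a) and (b) | Restart pembrolizumab | ALT | Normal or Grade 1 | Yes, if Grade 2 at baseline |
| 6.8.3(d) | Restart pembrolizumab | Laboratory values | Grade 1 | Yes |

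**Step 1. The like-for-like comparison.** Only the first two rows are hepatic taper rules. They differ in the baseline option and in what is judged.

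**Step 2. Apply both to a Grade 2 baseline.** Take a participant graded 2 at Cycle 1 Day 1 whose AST/ALT rises and then returns to exactly that value.
- Laboratory-grade reading of 6.8.1.6: Grade 2 is not Grade 1 or less, so the trigger is not met. Under 6.8.3(c) it is met, because the abnormal baseline has been regained.
- Symptom-only reading of 6.8.1.6: a participant without symptoms may taper, but 6.8.1.6 then has no laboratory criterion for the taper, whereas 6.8.3(c) requires one.

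The two rules disagree on either reading. If baseline was normal or Grade 1, a return to it satisfies both as far as laboratory grade goes, and the missing baseline option makes no difference.

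**Step 3. How far 6.8.3 and 7.4 reach.** This needs figures that the documents do not print. Assume that 3.5xULN is Grade 2 and that ULN is 40, 50 or 60 U/L. Consider a related rise from 3.5xULN to 4.8xULN.
- Size of rise: 4.8 / 3.5 = 1.37, or +37%.
- Footnote a limit: 1.5 x 3.5 = 5.25xULN. Not reached.
- 6.8.3(c) limit for a Day 1 value at or above 2xULN: the lower of 3 x 3.5 = 10.5xULN and 500 U/L. The latter is 500/40 = 12.5, 500/50 = 10 or 500/60 = 8.33xULN, so the limit is 10.5, 10 or 8.33xULN. Not reached.
- Section 7.4 item 2, drug-induced liver injury: AST or ALT at or above 3xULN. Reached, since 4.8 is above 3.

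Such a rise is below the laboratory levels listed in 6.8.3(c) but is an event of clinical interest under 7.4, and 6.8.1.6 sends hepatic events of interest to 6.8.3.

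**Step 4. The restart criterion.** Footnote a to Table 8 changes the discontinuation rule for Grade 2 starters but not the Grade 0-1 restart criterion. The restart rules in 6.8.3 do accept baseline grade; for hepatitis B flare, for example, ALT may return to normal or Grade 1 "or to baseline grade (if Grade 2 at baseline) within 12 weeks". Table 8 therefore has the same omission as 6.8.1.6.

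**The case against.** The strongest reply is that the sentence speaks of symptoms. Taken at its word, it does not stop an asymptomatic participant from tapering, and liver tests are handled by the separate monitoring instruction, which does use baseline. The same wording recurs for colitis and nephritis, so it looks like standard text. This stands in part: the conflict in its sharp form depends on reading the trigger as laboratory grade. But 6.8.1.6 organises care by event grade and follows liver tests, so that reading is a natural one, and the alternative leaves no laboratory criterion for the taper.

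The second reply is that the safeguards are adequate. Section 6.8.1 offers suggested measures, given as the investigator judges necessary; the sentence does not forbid an earlier taper; and Section 6.8.2 requires immediate discussion with the Chief Investigator or designee for immune-related events of Grade 2 or higher. This stands, and it keeps the point minor.

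A reader might go further and infer two things that the documents do not support.
- That smaller rises from a Grade 2 baseline fall under 6.8.1.6 with no other rule in play. Section 7.4 item 2 makes a related AST/ALT at or above 3xULN an event of clinical interest, and 6.8.1.6 points to 6.8.3. The thresholds in 6.8.3 say when immune-related hepatitis should be suspected, not that it may be considered only then.
- That baseline is the protocol's uniform standard because each hepatic recovery rule in 6.8.3 accepts it. Three of those rules, including the one for other hepatic events ("returned to Grade 1 or baseline (if normal or Grade 1 at start) or to baseline grade within 3 weeks"), concern restarting pembrolizumab. Table 8 and Table 10 have no baseline option. Only 6.8.3(c) is a true comparator.

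**Conclusion.** The point holds as a minor wording correction for participant safety. Sections 6.8.1.6 and 6.8.3(c) give different triggers for the same action, and the difference affects participants with Grade 2 AST/ALT at Cycle 1 Day 1, whom the protocol expressly expects. On the laboratory-grade reading, 6.8.1.6 would keep such a participant on steroid after full recovery to baseline.

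This conclusion needs no outside figure, because it follows from the participant being graded 2 on Day 1 and returning to that value. It does rest on the trigger being read as laboratory grade, and on the event being judged related to pembrolizumab, since Section 6.8.1 says: "The treatment guidelines are intended to be applied when the PI/delegate determines the events to be related to Pembrolizumab". The worked example in Step 3 rests on assumed grade and ULN values and serves only to show which rules are in play.

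The practical effect is small and the number of participants affected is unknown. No endpoint, DLT rule, sample size or analysis changes.

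**What to change.** In 6.8.1.6, let the taper start when symptoms and laboratory tests have improved to Grade 1 or less, or to the participant's own baseline if that was abnormal. This brings the trigger into line with 6.8.3(c) and removes the doubt over symptoms versus laboratory values. Add the same baseline option to the Table 8 restart criterion for Grade 2 AST/ALT, so that the steroid and restart rules agree. Leave the rules for starting steroid, the regimen and the discontinuation criteria as they are.

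The cost is two short changes in a protocol amendment, with no extra visits, tests or participants.

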6.8.2 Supportive Care Guidelines for Immune-related Adverse Event (irAE) and Immune-related Events of Clinical Interest (irECI).

Immune-related Adverse events (IrAEs) may be defined as an AE of unknown etiology, associated with IMP exposure and is consistent with an immune phenomenon. IrAEs may be predicted based on the nature of the Pembrolizumab compound, its mechanism of action, and reported experience with immunotherapies that have a similar mechanism of action. Special attention should be paid to AEs that may be suggestive of potential irAEs. An irAE can occur shortly after the first dose or several months after the last dose of IMP.

If an irAE is suspected, efforts should be made to rule out neoplastic, infectious, metabolic, toxin or other etiologic causes prior to labelling an AE as an irAE. Participants who develop a Grade 2 or higher irAE should be discussed immediately with the CI/designee.

Recommendations to managing irAEs not detailed elsewhere in the protocol are detailed in Table 10.

irAE	Withhold/Discontinue Pembrolizumab?	Supportive Care
Grade 1	No action	Provide symptomatic treatment
Grade 2	May withhold Pembrolizumab	Consider systemic corticosteroids in addition to appropriate symptomatic treatment. Steroid taper should be considered once symptoms improve to Grade 1 or less and tapered over at least 4 weeks.
Grade 3 and Grade 4	Withhold Pembrolizumab Discontinue if unable to reduce corticosteroid dose to < 10 mg per day prednisone equivalent within 12 weeks of toxicity	Systemic corticosteroids are indicated in addition to appropriate symptomatic treatment. May utilize 1 to 2 mg/kg prednisone or equivalent per day. Steroid taper should be considered once symptoms improve to Grade 1 or less and tapered over at least 4 weeks.

Table 10: General Approach for Handling irAEs

Details for managing specific irAEs are summarised below:

Immune-mediated pneumonitis

Monitor participants for signs and symptoms of pneumonitis. If pneumonitis is suspected, evaluate with radiographic imaging. Exclude other causes of pneumonitis, and manage treatment in accordance with the

guidelines above. Administer corticosteroids, withhold Pembrolizumab for moderate (Grade 2) pneumonitis, and permanently discontinue Pembrolizumab for severe (Grade 3) or life-threatening (Grade 4) pneumonitis.

Immune-mediated colitis

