7.2.1.1 Determining AE Severity and Grade

AE severity and grade will be evaluated according to the NCI CTCAE version 4.0. Any AE which changes CTCAE grade over the course of a given episode should be closed at the date and time the severity changed and a new AE recorded from the date and time of the new NCI CTCAE grade.

Grade 1	Mild; asymptomatic or mild symptoms; clinical or diagnostic observations only; intervention not indicated.
Grade 2	Moderate; minimal, local or non-invasive intervention indicated; limiting age-appropriate instrumental ADL.
Grade 3	Severe or medically significant but not immediately life-threatening; hospitalisation or prolongation of hospitalisation indicated; disabling; limiting self-care ADL.
Grade 4	Life threatening consequences; urgent intervention indicated.
Grade 5	Death related to AE

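### For immune-related events without a named rule, Table 10 leaves restart after Grade 4 open while Table 8 requires permanent discontinuation, and nothing says which table governs

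*Combined protocol and SAP*

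**What the plan says.** **Section 6.6 (Table 8).** The opening text is mandatory: "Pembrolizumab must be withheld for drug-related toxicities and severe or life-threatening AEs as per Table 8 below". Named rows cover colitis, liver tests, diabetes, hypophysitis, thyroid disease, infusion reactions, pneumonitis and nephritis. A last row, "All Other Drug-Related Toxicity", holds treatment at Grade 3 and ends it permanently at Grade 4. The note below the table adds: "Permanently discontinue for any severe or Grade 3 drug-related AE that recurs or any life-threatening event". Section 7.2.1.1 defines Grade 4 as "Life threatening consequences; urgent intervention indicated", so the note points the same way as the row.

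**Section 6.8.2 (Table 10).** The scope sentence reads: "Recommendations to managing irAEs not detailed elsewhere in the protocol are detailed in Table 10". Grades 3 and 4 share one row, whose dosing column says: "Withhold Pembrolizumab Discontinue if unable to reduce corticosteroid dose to < 10 mg per day prednisone equivalent within 12 weeks of toxicity".

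**Routing between the sections.** Section 6.8.1 says: "Refer to Section 6.6 for dose modification". Section 6.8.1.8 sends events of possible immunologic cause to 6.8.2 for diagnosis and management. Section 6.8.2 contains no reference back to 6.6. For immune-related events of clinical interest (irECIs, listed in Table 12 of section 7.4) that are judged related to the drug, it refers the reader to 6.8.3, the guidance on hepatic events.

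**The concern.** A participant may have a related Grade 4 event with no named row in Table 8 and no specific rule in 6.8.1 to 6.8.3, for example myocarditis, pancreatitis, Stevens-Johnson syndrome or toxic epidermal necrolysis, vasculitis or uveitis. An investigator who opens Table 8 stops pembrolizumab for good. One who follows 6.8.1.8 to Table 10 withholds it, and finds only a failed steroid taper as a reason not to resume.

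The stake is re-exposure after a life-threatening event. Section 1.2.2 reports one death among six myocarditis cases on this drug, and one fatal case each of Stevens-Johnson syndrome and toxic epidermal necrolysis. It also lists anthracyclines as a myocarditis risk factor. Every participant is to receive doxorubicin with TACE (section 6.1: 60 mg, or 75-150 mg with drug-eluting beads).

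**Working it through.** The core of this check is a comparison of text. The arithmetic only sizes the point, and the plan states no figure of its own here to reproduce.

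**1. The two rules for a related event without a named Table 8 row**

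| | Table 8, catch-all row and note | Table 10 |
|---|---|---|
| Grade 3 | Hold; restart at Grade 0-1 | Withhold; no restart criterion given |
| Grade 4 | Permanent discontinuation | Withhold, same row as Grade 3 |
| Steroid ground for stopping | Cannot reach 10 mg/day or less within 12 weeks | Cannot get below 10 mg/day within 12 weeks of the toxicity |
| Unresolved 12 weeks after last dose | Discontinue | Not mentioned |

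The steroid limits also differ: Table 8 discontinues for "inability to reduce corticosteroid to 10 mg or less of prednisone or equivalent per day within 12 weeks". A participant held at exactly 10 mg/day passes Table 8 and fails Table 10. This is minor.

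**2. Does Table 10's scope sentence settle it?** If Table 8's catch-all row counts as detail given elsewhere, Table 10's dosing column has no drug-related event left to govern. If it does not count, Table 10's dosing column applies and departs from Table 8 at Grade 4. The text does not say which.

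**3. Does the pointer settle it?** Table 12 names 21 terms: ocular 2 + renal 5 + skin at any grade 4 + skin at Grade 3 or above 5 + other 5. Only sclerosing cholangitis fits a hepatic section, so the pointer to 6.8.3 does not fit 21 − 1 = 20 of them. Removing the 5 renal terms, on which Table 8 and the nephritis text in 6.8.2 agree, leaves 20 − 5 = 15 terms with neither a named Table 8 row nor cover in 6.8.3. That is an upper bound for the Grade 4 conflict, because the documents do not give term-specific grades. The count includes the line for any clinically significant rash; without it, 14.

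**4. What does the rest of the protocol suggest?** Section 6.8.2 itself ends treatment for Grade 4 pneumonitis, colitis, nephritis and hyperthyroidism. It states its exceptions openly: withhold or discontinue for Grade 3 or 4 hypophysitis, and possible continuation after a Grade 3-4 endocrinopathy that has resolved and is controlled with hormone replacement. Table 8's hypophysitis and hyperglycaemia rows also allow resumption after Grade 4. So the Table 8 note is not absolute as it stands, and any repair must keep the endocrine exception.

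**5. Dosing consequence.** Cycles fall at weeks 0, 3, ..., 48, which is 17 doses. Suppose a Grade 4 event in week 2 and a full 12-week hold, to week 14. Under Table 8 no further dose is given. Under Table 10, if treatment resumes, doses at weeks 15 to 48 remain: (48 − 15)/3 + 1 = 12.

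**6. Frequency.** Section 1.2.2 gives 6 trial cases of Stevens-Johnson syndrome, 6 cases of myocarditis, and about 11,000 trial patients.
- Rate: 12/11,000 = 0.00109.
- Expected in 32 participants: 32 × 0.00109 = 0.035.
- Chance of at least one: 1 − (1 − 0.00109)^32 = 3.4%.

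These are events of any grade. The myocarditis count includes an expanded access programme, so the denominator is approximate. Section 6.8.2 puts uveitis and severe skin reactions below 1%, which is below 32 × 0.01 = 0.32 participants. The documents give no rate for pancreatitis or vasculitis.

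**The case against.** The strongest case is that Table 8 already governs. Section 6.6 owns dosing and uses mandatory language, 6.8.1 sends dose modification back to it, and 6.8.2 is titled as supportive care and offers recommendations. Even if Table 10's dosing column is set aside, its supportive-care column (steroid dose and taper) still has work to do. Permanent discontinuation also satisfies both tables, since Table 10 never says that a participant may restart after Grade 4.

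There are safeguards too. Symptomatic irECIs must stop treatment at once, Grade 2 or higher immune-related events are discussed immediately with the chief investigator, and questions on irECI management go to the chief investigator or delegate.

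Most of this stands, and it limits the point. A reader might infer that the tables state opposite rules, or that the protocol authorises restart after Grade 4. The documents do not support that: Table 10 is silent on restart. The silence still matters, because Table 10 has its own column on withholding and discontinuing, lists one ground for the latter, and is where 6.8.1.8 sends the reader. The immediate stop is not said to be permanent, and the chief investigator has the same two tables.

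A reader might also infer damage to the primary endpoint, because section 8.3 summarises adverse events by their effect on study drug. One participant handled differently moves a discontinuation rate by 1/32 = 3.1 percentage points. But section 7.2 records the action actually taken, so the report would be accurate, and the number of Grade 4 events does not depend on the table used.

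**Conclusion.** The plan is wrong as written on this point and should be corrected. For drug-related immune-related events with no named row and no specific rule, Table 10 leaves restart after Grade 4 open where Table 8 closes it. Table 8 is the likely intention, but the text does not say so, and the irECI pointer leads to a section that does not apply.

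The practical size is small in frequency and potentially serious for an individual. Myocarditis and Stevens-Johnson syndrome together give about 0.03 expected participants in 32 at any grade, assuming that the cited counts carry over to this population after TACE, which the documents cannot confirm. A larger frequency might be inferred from the cited 6.8-12.0% rate of Grade 3-5 drug-related events. That would need the share that is Grade 4 and falls in this group, which the documents do not give. Of the four commonest such events listed in 1.2.2, three (raised ALT, raised AST and colitis) have their own Table 8 rows.

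The benefit is participant safety and consistent dosing. No hypothesis test or stopping rule is affected.

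**What to change.** 1. Split the combined row in Table 10.
   - Grade 4: permanently discontinue, as in Table 8. The exception is endocrinopathy that has resolved and is controlled with hormone replacement, where the existing 6.8.2 allowance and Table 8's hypophysitis and hyperglycaemia rows stay in force.
   - Grade 3: withhold, with restart and discontinuation as in Table 8's catch-all row (resolution to Grade 0-1; steroid at 10 mg/day or less within 12 weeks).
2. State in 6.8.2 that Table 8 governs dosing wherever it differs from Table 10, subject to that endocrine exception.
3. Add the same exception to the note under Table 8.
4. Redirect related non-hepatic irECIs to 6.6 and Table 8 for dosing and to Table 10 for supportive care. Hepatic events stay with 6.8.3.
5. If the sponsor wants restart after any other Grade 4 event, name it in Table 8 as an exception.

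The cost is one table row and a few sentences, submitted as an amendment under section 9.3.2. No visits, tests or data are added. Some participants who might have been restarted under Table 10 would not be, which is already Table 8's rule.
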